## 7.2. Secondary Efficacy Analyses

### 7.2.1. Endpoint / Variables

The secondary endpoints are:

- Change and % change from baseline in appendicular, and total lean mass as assessed by Dual-energy X-ray Absorptiometry (DXA).
- Change from baseline in total Short Physical Performance Battery (SPPB) score, times for chair rise and 4 m gait speed.

- Change and % change from baseline in Constant Work Rate (CWR) duration from endurance shuttle walking test.
- Change and % change from baseline in peak performance from incremental shuttle walking test.
- Change in PROactive endpoints (individual components (difficulty and amount score) and total score).
- Change from baseline in COPD Assessment Test (CAT).
- Responder of COPD Assessment Test (CAT).
- Change in St George Respiratory Questionnaire (SGRQ) total score and domain scores derived from SGRQ-c raw score.
- Responder of St George Respiratory Questionnaire (SGRQ) defined by the total score.
- Change from baseline in forced expiratory volume in 1 second (FEV1).
- Patient Global Impression of Change (PGIC).
- Patient Global Rating of Severity (PGRS).
- Change from baseline in Sniff nasal inspiratory pressure (SnIP).
- Change in physical activity measures as assessed via an accelerometer.

### 7.2.2. Summary Measure

The adjusted mean treatment differences (GSK2881078 – Placebo) for the following endpoints will be presented:

- Change and % change from baseline in appendicular, and total lean mass as assessed by Dual-energy X-ray Absorptiometry (DXA) at Days 28, 56 and 90.
- Change from baseline in total Short Physical Performance Battery (SPPB) score, times for chair rise and 4 m gait speed at Days 28, 56 and 90.
- Change and % change from baseline in Constant Work Rate (CWR) duration from endurance shuttle walking test at Day 90.
- Change and % change from baseline in peak performance from incremental shuttle walking test at Day 90.
- Change from baseline in PROactive endpoints at Days 56 and 90. (individual components and total score).
- Change from baseline in COPD Assessment Test (CAT) score at Days 56 and 90.
- Change from baseline in St George Respiratory Questionnaire (SGRQ) total score and domain scores derived from SGRQ-c raw scores at Days 90.

The responder analysis between GSK2881078 and Placebo (GSK2881078/ Placebo) for the following endpoints will be explored

- Odds ratio between treatment groups for the COPD Assessment Test (CAT) responder at Days 56 and 90.
- Odds ratio between treatment groups for the St George Respiratory Questionnaire (SGRQ) responder defined by the total score derived from SGRQ-c raw scores at Days 90.

The descriptive summaries will be reported for the following endpoints

- Change from baseline in forced expiratory volume in 1 second (FEV1).

- Frequency and percentages of Patient Global Impression of Change (PGIC) responses.
- Frequency and percentages of Patient Global Rating of Severity (PGRS) responses.
- Change from baseline in Sniff nasal inspiratory pressure (SnIP).
- Change in physical activity measures as assessed via an accelerometer.

**7.2.3. Population of Interest**

The secondary efficacy analyses will be based on the Analysis Population. The decision-making endpoints PROactive endpoint, SGRQ, SPPB (time for repeated chair rise endpoint) and constant work rate (CWR) duration from endurance shuttle walking test will be also analysed based on the Per Protocol population.

**7.2.4. Statistical Analyses / Methods**

Details of the planned displays are provided in [Appendix 11](#): List of Data Displays and will be based on GSK data standards and statistical principles.

Unless otherwise specified, endpoints / variables defined in [Section 7.2.1](#) will be summarised using descriptive statistics, graphically presented (where appropriate) and listed.

**7.2.4.1. Statistical Methodology Specification**

Secondary Efficacy Endpoint / Variables – Multiple Post-baseline Visit

 
• Change and % change from baseline in appendicular, and total lean mass as assessed by Dual-energy X-ray Absorptiometry (DXA) at Days 28, 56 and 90.
 
• Change from baseline in total Short Physical Performance Battery (SPPB) score, **time for repeated chair rise and 4 m gait speed at Days 28, 56 and 90.
 
• Change from baseline (Day 1) in *PROactive endpoints (individual components (difficulty and amount score) and **total score) at Days 56 and 90.
 
• Change from baseline in COPD Assessment Test (CAT) score at Days 56 and 90.
 
 
*A physical activity monitor will be worn for 7 days after the Day -9 visit (Day 1), for 7 days after the Day 56 visit (Day 56), and for 7 days following the day 80 visit (Day 90).
 
**Bayesian analysis will be performed only for the endpoints change from baseline of PROactive total scores and change from baseline in the time for repeated chair rise. The posterior probability of treatment difference greater than 3 points and less than 6 points for PROactive total scores and greater than 1.3 seconds and less than 1.7 seconds for time for repeated chair rise will be estimated for each visit separately by gender.

Model Specification

 
• Treatment difference (GSK2881078 – placebo) at each visit on change from baseline or percentage change from baseline (as appropriate) will be analysed using mixed models repeated measures (MMRM) models as what was described for the primary efficacy endpoint in Section 7.1.4.1. The analyses will be based on the analysis population for all endpoints additionally the endpoints PROactive and SPPB will be analysed for per-protocol population as well.
 
• If there are any departures from the distributional assumptions for change or percentage change from baseline, the change of log-transformed data at post- baseline from log baseline will be the response variable, adjusted for treatment, log-transformed baseline value, day and
 


the interaction of treatment and day, with day as the repeated factor.
 
 
• A Bayesian approach will also be employed for the change from baseline in PROactive weekly total score and time for repeated chair rise to estimate the treatment difference in the change from baseline for analysis population, following the similar procedures described in Section 7.1.4.1. for the primary efficacy endpoint analysis. For calculating the posterior adjusted least square mean and corresponding difference, use the coefficient of L-matrix of the covariates from the corresponding frequentist MMRM analysis.
 

Model Checking & Diagnostics

 
• Refer to Appendix 9: Model Checking and Diagnostics for Statistical Analyses.
 

Model Results Presentation


 
• For change and percent change from baseline, adjusted means and corresponding standard error of means (SEs) and 90% confidence intervals will be presented for each treatment by gender and then by time, together with estimated treatment differences (GSK2881078 – Placebo) and the corresponding 90% confidence intervals for MMRM estimation.
 
• In case of the violation of assumptions in MMRM analysis, adjusted mean for ratio to baseline and 90% confidence intervals will be presented for each treatment by gender and then by time, together with adjusted treatment ratio of the ratio (postbaseline value/baseline value) between the two treatments with the corresponding 90% confidence interval be presented by day.
 
• A line plot of the adjusted mean change from baseline or percentage change from baseline (as appropriate) as well as 90% confidence intervals over time (day) for each treatment by gender from the MMRM model will be provided for the analysis population. In case of violation of assumption in MMRM analysis, the adjusted mean for ratio to baseline and corresponding 90% confidence interval will be plotted.
 
• For the Bayesian analysis, n, posterior adjusted least square mean and 90% highest posterior density (HPD) interval, the adjusted treatment difference and its 90% HPD credible interval and standard deviation for the posterior adjusted least square mean and difference will be reported along with the estimated probabilities.
 
• For the Bayesian analysis for PROactive weekly total score, the probability of treatment difference (GSK2881078-placebo) greater than 3 points and less than 6 points will be estimated through the simulations of the posterior probability distribution. Similarly, for the Bayesian analysis for time for repeated chair rise, the probability of treatment difference (GSK2881078-placebo) greater than 1.3 seconds and less than 1.7 seconds will be estimated through the simulations of the posterior probability distribution.
 

Secondary Efficacy Endpoint / Variables – Categorical Variable

 
• Odds ratio of COPD Assessment Test (CAT) responder at Days 56 and 90.
 
• Odds ratio of St George Respiratory Questionnaire (SGRQ) responder derived by the total score at Days 90.
 

Model Results Presentation


 
• The number of responders, odds ratio and associated 90% exact confidence intervals between treatment groups (GSK2881078 vs. placebo) will be reported for CAT and SGRQ responder analysis by gender.
 

Secondary Efficacy Endpoint / Variables – Single Post-baseline Visit

 
• Change and % change from baseline in Constant Work Rate (CWR) duration* from endurance shuttle walking test at Day 90.
 
• Change and % change from baseline in peak performance from incremental shuttle walking test at Day 90.
 
• Change from baseline in St George Respiratory Questionnaire (SGRQ) total score* and domain scores derived from SGRQ-c raw scores at Days 90.
 
 
*Bayesian analysis will be performed only for the endpoints change from baseline of Constant Work Rate (CWR) duration and change from baseline of SGRQ total score. The posterior probability of treatment difference greater than 36 seconds and less than 48 seconds for Constant Work Rate (CWR) duration and greater than 2 points and less than 4 points SGRQ total score will be estimated.

Model Specification

 
• Treatment difference (GSK2881078 – placebo) in the change from baseline and percentage change from baseline at Day 90 will be analysed using ANCOVA where baseline and treatment will be included as the independent variables in the model. Each gender will be analysed separately. The analyses will be based on the analysis population for the endpoints CWR duration, peak performance from incremental shuttle walking test and SGRQ total score additionally the endpoints CWR duration and SGRQ total score will be analysed for per-protocol population as well.
 
• If there are any departures from the distributional assumptions, the change of log-transformed data at post- baseline from log baseline will be the response variable, adjusted for treatment, and log-transformed baseline value.
 
• A Bayesian approach will also be conducted to estimate the treatment difference in the change from baseline at Day 90 for CWR duration and change from baseline SGRQ total score for the analysis population, following the similar procedures described in Section 7.1.4.1. for the primary efficacy endpoint analysis with the model being constructed as below:
 
• Create indicator variables for the categorical effect: Treatment (GSK2881078 vs. Placebo). For treatment, if treatment=placebo, then drug=0; if treatment=GSK2881078, then drug=1;
 
• For subject i on treatment j, the model can be written as:  <math display="block">CH_{ij} = \beta_0 + \beta_1 \text{ drug} + \beta_2 \text{ base} + \epsilon_{ij}</math>                     where CH refers to the change from baseline at Day 90; base means baseline assessment; drug=0 when treatment is placebo and drug=1 for GSK2881078 treatment; <math>\epsilon_{ij} \sim N(0, \sigma^2)</math>; <math>\beta_1</math> is the estimated treatment difference (GSK2881078 vs. placebo) at Day 90;
 
• Set seed=123456 with the simulation size of 200000 and 5000 burn-in iterations; the sample size and the number of burn-in iterations could be updated during the convergence check.
 
• The non-informative priors (normal (0, var=1e6)) will be used for the regression parameters <math>\beta_0</math>, <math>\beta_1</math>, and <math>\beta_2</math>. and the prior for variance <math>\sigma^2</math> will be the inverse gamma (0.01, scale=0.01)
 
• For calculating the posterior adjusted least square mean and corresponding difference, use the coefficient of L-matrix of the covariates from the corresponding ANCOVA analysis
 

Model Checking & Diagnostics

 
• Refer to Appendix 9: Model Checking and Diagnostics for Statistical Analyses.
 

**Model Results Presentation**

- For change and percent change from baseline, adjusted means and corresponding standard error of means (SEs) and 90% confidence intervals will be presented for each treatment at Day 90, together with estimated treatment differences (GSK2881078 – Placebo) and the corresponding 90% confidence intervals through ANCOVA model.
- In case of the violation of assumptions in ANCOVA analysis, adjusted mean for ratio to baseline and 90% confidence intervals will be presented for each treatment by gender, together with adjusted treatment ratio of the ratio (postbaseline value/baseline value) between the two treatments with the corresponding 90% confidence interval be presented.
- For the Bayesian analysis, n, posterior adjusted least square mean and 90% highest posterior density (HPD) interval, the adjusted treatment difference and its 90% HPD credible interval and standard deviation for the posterior adjusted least square mean and difference will be reported along with the estimated probabilities.
- For the Bayesian analysis for CWR duration, the probability of treatment difference (GSK2881078-placebo) greater than 36 seconds and less than 48 seconds will be estimated through the simulations of the posterior probability distribution. Similarly, for the Bayesian analysis for SGRQ total score, the probability of treatment difference (GSK2881078-placebo) greater than 2 points and less than 4 points will be estimated through the simulations of the posterior probability distribution.

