
 
For change and percent change from baseline, adjusted means, corresponding standard error of means (SEs) and 90% confidence intervals will be presented for each treatment by day, together with estimated treatment differences (GSK2881078 – Placebo) and the corresponding 90% confidence intervals and p-value by day for both Analysis and Per Protocol population.
 
A line plot of the adjusted mean of change (and percentage change) from baseline as well as the 90% confidence interval over time (day) for each treatment from the MMRM model will be provided for the analysis population.
 
 
Log-transformed data results presentation
 
 
The estimated coefficients of the MMRM model will be transformed back (exponential transform).
 
For each treatment, adjusted ratio of the post baseline value to the baseline value and corresponding 90% confidence intervals will be presented by day.
 
The adjusted treatment ratio of the ratio (postbaseline value/baseline value) between the two treatments with the corresponding 90% confidence interval be presented by day.
 
The plot of adjusted ratio of the post baseline value to the baseline value and its 90% confidence interval over time (day) for each treatment arm will be presented for the analysis population
 

Supportive Statistical Analysis - Bayesian

 
% change from baseline in maximum leg press strength following 1 repetition maximum (1-RM) at Days 28, 56 and 90 will be estimated by Bayesian analysis and separately by gender.
 
The posterior probability of treatment difference greater than 4% points, less than 9% points and greater than or equal to 9% points for each visit separately by gender.
 

Model Specification

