## 12.6. Appendix 6: Derived and Transformed Data

### 12.6.1. General

Multiple Measurements at One Analysis Time Point

 
• Mean of the measurements (not in case of visit slotting) will be calculated and used in any derivation of summary statistics but if listed, all data will be presented.
 
• If there are two values within a time window (as per Section 12.3.1) the value closest to the target day for that window will be used. If values are the same distance from the target, then the mean will be taken.
 
• Participants having both High and Low values for Normal Ranges at any post-baseline visit for safety parameters will be counted in both the High and Low categories of “Any visit post-baseline” row of related summary tables. This will also be applicable to relevant Potential Clinical Importance summary tables.
 

Study Day

 
• Calculated as the number of days from First Dose Date: 
 
• Ref Date = Missing → Study Day = Missing
 
• Ref Date < First Dose Date → Study Day = Ref Date – First Dose Date
 
• Ref Date ≥ First Dose Date → Study Day = Ref Date – (First Dose Date) + 1
 
 
 
 
Note that Treatment Start Date is considered as Study Day 1.

Post-baseline

 
• Post-baseline refers to the combined time periods of On-treatment and Post-treatment.
 

Change from Baseline
= Post-baseline - Baseline
Ratio to Baseline
= $\exp(\log(\text{Post-baseline}) - \log(\text{Baseline}))$
Percent Change from Baseline
= $100 * (\text{Post-baseline} - \text{Baseline}) / \text{Baseline}$
Treatment compliance

= <math>100 * (\text{Total Amount Taken} / (\text{Treatment duration in days} * 2))</math>
 
Total Amount Taken = Total tablets dispensed – Total tablets returned – Total tablets lost.

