Activity: The Activity component will tolerate a maximum of 3 missed items. The weight for the missed item (s) is subtracted from the total possible weight for the Activity component (982.9) and from the Total weight (3201.9) and then calculate the score.  
Impacts: The Impacts component will tolerate a maximum of 5 missed items. The weight for the missed item (s) is subtracted from the total possible weight for the Impacts component (1652.8) and from the Total weight (3201.9) and then calculate the score.
- Responder is defined as 'Yes' when the total score at a post-baseline visit decreases by 4 or more from baseline total score, otherwise, non-responder.

Secondary Efficacy endpoints		
Total Short Physical Performance Battery (SPPB) score and times for chair rise and 4 m gait speed		

 
Total SPPB score, 'Time for five stands done successfully' collected for chair and 'time for fastest walk for 4 m gait test' collected from CRF will be used, respectively
 
SPPB at baseline will be categorized as below: SPPB 10-12 points fit patient, normal  SPPB 8-9 points pre-frail patient  SPPB ≤ 7 points frail patient
 
		
COPD Assessment Test (CAT)		

 
Total score of 8 questions will be used
 
Responder is defined as 'Yes' when the total score at a post-baseline visit decreases by 2 or more from baseline total score, otherwise, non-responder.
 
If one or more of the 8 questions are missing the total score and the responder will be missing.
 
		
PROactive endpoints (individual components (Difficulty and Amount) and total score)		

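### The Bayesian thresholds for SGRQ total score and repeated chair-rise time sit on the harm side of zero

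*SAP*

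**What the plan says.** SAP 7.2.4.1 gives the SGRQ thresholds twice. The single-visit endpoint list has "greater than 2 points and less than 4 points SGRQ total score will be estimated", and the results presentation has "for SGRQ total score, the probability of treatment difference (GSK2881078-placebo) greater than 2 points and less than 4 points will be estimated". Chair rise is also stated twice: "greater than 1.3 seconds and less than 1.7 seconds for time for repeated chair rise will be estimated for each visit separately by gender" in the multiple-visit endpoint list, and "for time for repeated chair rise, the probability of treatment difference (GSK2881078-placebo) greater than 1.3 seconds and less than 1.7 seconds will be estimated" in the results presentation.

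The sign convention is fixed elsewhere in the SAP. Section 12.6.1 defines change from baseline as "Post-baseline - Baseline". The Bayesian model in 7.2.4.1 codes placebo as 0 and GSK2881078 as 1, so the treatment coefficient is active minus placebo.

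The direction of benefit for SGRQ is explicit. Protocol 9.2.4.2 runs the scale from no impairment at 0 up to the worst state, and SAP 12.6.2 counts a responder "when the total score at a post-baseline visit decreases by 4 or more from baseline total score". Chair rise is "Time for five stands done successfully" (SAP 12.6.2), a duration in seconds.

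For the primary strength endpoint, SAP 7.1.4.1 uses the same threshold form: "The posterior probability of treatment difference greater than 4% points, less than 9% points and greater than or equal to 9% points".

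**The concern.** The strength wording works because more strength is better: one probability for exceeding a minimum effect, one for missing the target and one for reaching it. For SGRQ and chair rise the form was carried over without turning the sign. In the results presentation the SGRQ sentence follows directly from the one for CWR duration, where a longer time is better.

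The wording also leaves open whether the two limits mean one interval or two one-sided probabilities. Neither reading measures benefit:

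- **One interval.** P(2 < d < 4) lies wholly in the region where the drug is worse than placebo.
- **Two one-sided probabilities.** P(d > 2) is the probability of worsening by more than 2 points. P(d < 4) approaches 1 for an effective drug, so it cannot serve as a target-missed probability.

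SAP 7.2.3 names both as decision-making endpoints. SAP Table 1 (section 2.1) ties such endpoints to a univariate Bayesian analysis and a prospectively defined decision framework. Tables 2.23 and 2.28 are marked as headline results. A team reading those rows under the convention used for strength would see an effective drug score near 0 and a harmful one score high.

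**Working it through.** **Direction.** Let d be the difference in mean change, GSK2881078 minus placebo. A benefit equal to the SAP's own SGRQ responder size is d = -4. The SGRQ-C to SGRQ conversion for the total score (SAP 12.6.2) has slope +0.90, so it does not reverse direction. Faster chair rise also means d < 0. No passage recodes change as improvement or calls the thresholds absolute magnitudes.

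**Plan's own precision figure.** The documents give no SD for SGRQ or chair rise, so I first checked the precision method on strength (protocol 10.1.1, SD 10.9). Half-width of the 90% CI = t(0.95, 2n-2) × SD × √(2/n):

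- n = 10: 1.734 × 10.9 × √0.2 = 8.45 (stated 8.45)
- n = 20: 1.686 × 10.9 × √0.1 = 5.81 (stated 5.8)

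**Posterior probabilities.** Inputs are 20 evaluable per arm within each sex (protocol 5.2) and near-flat normal priors with variance 1e6 (SAP 7.2.4.1). The SDs of change are my assumptions. The posterior of d is approximated as t with 37 df, centred on the observed difference, with standard error SD × √(2/20). For chair rise this treats one visit alone rather than the full repeated-measures model.

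SGRQ, standard errors 2.53, 3.79 and 5.06 for SD 8, 12 and 16:

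| Observed d | Probability | SD 8 | SD 12 | SD 16 |
|---|---|---|---|---|
| -4 (benefit) | as written, P(d > 2) | 0.012 | 0.061 | 0.122 |
| -4 | as written, P(d < 4) | 0.998 | 0.979 | 0.939 |
| -4 | as written, P(2 < d < 4) | 0.010 | 0.040 | 0.060 |
| -4 | sign reversed, P(d < -2) | 0.783 | 0.699 | 0.653 |
| -4 | sign reversed, P(d > -4) | 0.500 | 0.500 | 0.500 |
| -8 (larger benefit) | as written, P(d < 4) | 1.000 | 0.998 | 0.988 |
| -8 | sign reversed, P(d > -4) | 0.061 | 0.149 | 0.217 |
| +4 (harm) | as written, P(d > 2) | 0.783 | 0.699 | 0.653 |

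Chair rise, standard errors 0.63, 1.26 and 1.90 s for SD 2, 4 and 6 s:

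| Observed d | Probability | SD 2 | SD 4 | SD 6 |
|---|---|---|---|---|
| -1.7 s (benefit) | as written, P(d > 1.3) | 0.000 | 0.012 | 0.061 |
| -1.7 s | as written, P(d < 1.7) | 1.000 | 0.995 | 0.959 |
| -1.7 s | sign reversed, P(d < -1.3) | 0.735 | 0.623 | 0.583 |
| +1.7 s (harm) | as written, P(d > 1.3) | 0.735 | 0.623 | 0.583 |

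A Gibbs run with the SAP's stated priors for the single-visit model (SGRQ, SD 12, observed d = -4) gave P(d > 2) = 0.062, P(d < 4) = 0.979 and P(d < -2) = 0.696. This agrees with the approximation.

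**The case against.** The best defence concerns weight rather than sign.

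- **Key endpoint.** SAP 5.5 and 7.1.2 make percent change in leg press strength the key decision endpoint, and 5.5 ties study success to that analysis in both sexes. SGRQ and chair rise are secondary, and the decision framework itself is not in the supplied documents. This stands and limits severity.
- **Recoverable.** The signed posterior difference, its SD and the 90% HPD interval are reported beside the probabilities. A careful reader could notice the reversal and approximate the right figure. This also stands, but the prespecified probability would still be wrong.
- **Table shell.** Most of the Bayesian shell (EFF_T2) is missing from the extract, so a corrected sign there cannot be excluded. Its surviving footnote repeats the active-minus-placebo difference, and four explicit statements in 7.2.4.1 carry the positive limits.
- **Other thresholds.** SAP 2.4 promises additional threshold values for decision-making endpoints but gives none, so it does not repair the sign.
- **Intent.** The authors may have meant sizes of improvement. The text does not say so, and the results-presentation sentences name the signed difference.
- **Support.** The documents never state that a shorter chair-rise time is better; that follows from the measure. They anchor only the 4-point SGRQ value.

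**Conclusion.** The concern holds. On the SAP's own definitions, both pairs of thresholds are on the wrong side of zero. For an observed SGRQ benefit of 4 points, the planned P(d > 2) is about 1% to 12%, against 65% to 78% for the correctly signed probability. If the drug were 4 points worse, the planned figure would itself be 65% to 78%. Chair rise behaves the same way.

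The direction of the error does not depend on any assumption for SGRQ. For chair rise it needs only that a shorter time is better. The sizes rest on 20 per arm and the assumed SDs, and are illustrative.

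This should be fixed, but it does not threaten the primary result. The error lies in prespecified headline quantities, not in a decision rule that the documents show. The ANCOVA and MMRM estimates, the HPD intervals, the SGRQ responder analysis and the strength analysis are unaffected.

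**What to change.** In all four statements in SAP 7.2.4.1, reverse the signs and say that the limits are separate one-sided probabilities, as is done for strength:

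- **SGRQ total score:** P(d < -2) and P(d > -4), optionally with P(d ≤ -4).
- **Repeated chair-rise time:** P(d < -1.3 s) and P(d > -1.7 s), optionally with P(d ≤ -1.7 s).

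Carry these into Tables 2.23 and 2.28 and their shell. Keep the difference as GSK2881078 minus placebo, so that the Bayesian tables agree in sign with the ANCOVA and MMRM tables (2.20 and 2.26). CWR duration and PROactive use the same two-limit wording, so clarify there too that the limits are separate probabilities.

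The cost is four text edits and about one line of code per endpoint, using the same posterior draws and no new data. Make the change before the final unblinding, and record that it follows from the SAP's existing definitions, so that it cannot be taken for a response to the results.
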